4.1.2 SECONDARY ENDPOINT

- Number of grade II or higher adverse events (AE) through day 21 of study
- Levels of various components of the RAS system including Ang(1-12), AngI, AngII and Ang(1-7)
- Levels of various blood biomarkers

4.1.3 EXPLORATORY ENDPOINTS

- SARS-CoV-2 detectability in OP samples

5 STUDY ENROLLMENT AND WITHDRAWAL

5.1 PARTICIPANT INCLUSION CRITERIA

- Able to provide written informed consent prior to initiation of any study procedures.
- Understands and agrees to comply with planned study procedures including self testing of blood pressure daily
- Male or non-pregnant female adult ≥ 18 years of age at time of enrolment.
- Subject reported positive SARS-CoV-2 test by a commercial laboratory or public health assay in any specimen collected ideally < 72 hours prior to randomization. Exceptions to the < 72 hr inclusion criteria may be made at the discretion of the investigator.
- Positive for COVID-19 symptoms: **fever** defined as a temperature of ≥ 100.4 on study screening or self-report of daily fever at home OR **shortness of breath** of any degree OR **fatigue** causing greater than minimal interference with usual social & functional activities
- Women of childbearing potential must agree to use at least one primary form of contraception for the duration of the study
- Able to easily swallow pills

5.2 PARTICIPANT EXCLUSION CRITERIA

- Immediate need for hospitalization on screening
- Systolic blood pressure less than 100 mmHg
- Self-reported presence of chronic kidney disease or requiring dialysis
- Self-reported history of liver failure or untreated hepatitis B or C
- Pregnancy or breast feeding
- Allergy to the study medication
- Current use of ARB or ACE Inhibitor medications. Other blood pressure medications will be permitted in the systolic BP is higher than 90 mmHg
- Prior reaction or intolerance to ARB or ACE Inhibitor
- Use of aliskiren participant
- Current use of and on-going need for lithium, digoxin, potassium sparing diuretics such as spironolactone
- Current use of and need for potassium supplements
- Current or past participation in a research study within 12 weeks prior to the Screening Visit unless cleared by Study Team
- Inability to arrange a safe environment for study visits
- Subjects, who, in the opinion of the investigator, are unable to comply with the protocol evaluation, or for whom study participation may not be advisable

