2.2.2 KNOWN POTENTIAL BENEFITS

Telmisartan is indicated for the treatment of hypertension, to lower blood pressure. Lowering blood pressure reduces the risk of fatal and nonfatal cardiovascular events, primarily strokes and myocardial infarctions. According to the package insert, the antihypertensive effects of Telmisartan have been demonstrated in six principal placebo-controlled clinical trials, studying a range of 20 to 160 mg; one of these examined the antihypertensive effects of Telmisartan and hydrochlorothiazide in combination. The studies involved a total of 1773 patients with mild to moderate hypertension (diastolic blood pressure of 95 to 114 mmHg), 1031 of whom were treated with Telmisartan. Following once daily administration of Telmisartan, the magnitude of blood pressure reduction from baseline after placebo subtraction was approximately (SBP/DBP) 6 to 8/6 mmHg for 20 mg, 9 to 13/6 to 8 mmHg for 40 mg, and 12 to 13/7 to 8 mmHg for 80 mg. Larger doses (up to 160 mg) did not appear to cause a further decrease in blood pressure.

Some beneficial effects not related to its anti-hypertensive effects have also been reported at least for ARB medications in general. ARB medications have been reported to suppress mediators of inflammation, including ROS and C-reactive protein, and they increase expression of inhibitory κ B (an inhibitor of nuclear factor- κ B)^{21,22}. It has also been reported that the use of ARBs lower progression of emphysema and lower incidence of inflammatory complications including rates of pneumonia and influenza⁹. In animal models, inhibition of AT₁ signaling has been shown to attenuate experimental pulmonary fibrosis induced by bleomycin, radiation, and hyperoxia. In a pilot clinical study, Couluris et al. evaluated the effect losartan, an AT₁ antagonist, on idiopathic pulmonary fibrosis progression over 12 months²³. The study demonstrated stable or improved pulmonary function testing in 12 of the 17 patients treated with losartan. The authors concluded that losartan is a promising low-toxicity agent for treatment of idiopathic pulmonary fibrosis that requires more extensive evaluation in a placebo-controlled multicenter trial.

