6.1.6 STARTING DOSE AND DOSE ESCALATION SCHEDULE

Participants will be randomized to one 40 mg tablet of Telmisartan daily or one placebo tablet daily. There is no dose reduction or escalation for this study.

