- The current signs and symptoms will be reviewed and the presence of symptoms sufficient to meet entry requirements will be confirmed. Entry Symptom Scale and Clinical Status to be recorded.
- A photo of the person's COVID-19 test result will be taken. If unavailable and the person opts to have the researchers request it, the person will provide signed permission Consent to Release Information and a photo will be taken of the document. This will permit researchers to obtain the test result document. Also, the person will be asked to sign the Consent to Release in case of hospitalization.

With confirmation of study eligibility:

- Vitals signs will be taken to include temperature, pulse, blood pressure, respiratory rate, and O₂ sat.
- Oro-pharyngeal swab will be obtained
- Blood draw for clinical safety labs and for research assays in quantity as specified in the Schedule of Events.
- The participant will be given a Symptoms log and instructed to daily take and record his/her own blood pressure and temperature. Temperature should also be taken whenever there is tactile fever. The participant will be provided with a digital thermometer and BP monitor as needed and instructed in their use. The participant will be asked to call *immediately* if systolic blood pressure falls below 90 mmHg and to NOT take further study medications unless advised by the study team that it is safe to do so.
- The pharmacist will randomize study participant to telmisartan or placebo; then the study medication will be dispensed to the participant. Participant will be instructed to take first dose as soon as he or she is home.
- Provide the following instructions to participants:
 - Take BP daily at generally the same time of the day and record on Symptoms log. Call research team if SBP is <90 and do not take further study medication unless instructed to do so by the research team.
 - Take temperature whenever a fever is suspected but at least once daily and record
 - Record appropriate fever, dyspnea and fatigue symptoms daily
 - Record the time study medication is taken daily
 - Participants will be advised to take particular effort to remain hydrated, and to be judicious with the use of aspirin or other NSAIDS for fever/symptomatic treatment because it may increase risk for renal problems if excessive amounts are taken with study medication.

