6.5 CONCOMITANT MEDICATIONS, TREATMENTS, AND PROCEDURES

The participant's 'usual medications' may be continued unless specifically contra-indicated in this study. Antipyretics and other symptomatic medications and treatments will be allowed although participants will be asked to use judiciously and in moderation. The participant will be asked to call the Study Team if/when antibiotics or other medications are prescribed by the participant's own physician. In general these will be allowed except if drug-drug interaction with Telmisartan or if increased toxicity is of concern.

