 - Modifying a study without prior IRB approval unless to remove an apparent immediate hazard to one or more study participants.
 - Enrollment of a subject who did not meet any inclusion/exclusion criteria.
 - Failure to perform a required procedure, assessment, or lab test that, in the opinion of the PI, may affect the safety or welfare of one or more participants or the integrity of the data collected.
 - A drug dispensing or dosing error.
 - A study visit conducted outside of the required time period with a potentially adverse effect on the safety or welfare of one or more study participants.
 - Failure to follow applicable federal regulations or IRB policies and procedures, including those for reporting Unanticipated Problems and Adverse Events.
 - Failure to follow an IRB-approved safety monitoring plan.

Corrective Action Plan (CAP) is defined as a plan developed in response to a protocol violation that outlines the steps to be taken to: (1) reduce the risk to participants affected by the violation, and (2) prevent a recurrence of the violation.

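### Section 5.2 gives two unreconciled systolic BP thresholds, 100 mmHg and 90 mmHg; one floor should be stated

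*Combined protocol and SAP*

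**What the plan says.** Section 5.2 (Participant Exclusion Criteria) lists as a stand-alone exclusion "Systolic blood pressure less than 100 mmHg", with no exception attached. Further down the same list, the bullet excluding current ARB or ACE inhibitor users ends with "Other blood pressure medications will be permitted in the systolic BP is higher than 90 mmHg". I take the word 'in' there as a slip for 'if'.

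Three other places bear on the point:

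- Section 6.4.6 instructs participants: "Call research team if SBP is <90 and do not take further study medication unless instructed to do so by the research team".
- Section 6.5 says that a participant's usual medications "may be continued unless specifically contra-indicated in this study". Neither it nor section 6.6, on prohibited drugs, gives a BP threshold.
- Section 12.3.1 lists among major protocol violations: "Enrollment of a subject who did not meet any inclusion/exclusion criteria".

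**The concern.** Telmisartan lowers blood pressure, so the systolic floor at entry is a safety criterion. Section 5.2 attaches two numbers to it. For a patient on, say, a calcium-channel blocker with a systolic reading of 95 mmHg, site staff could find support in the same list for opposite decisions. If 100 mmHg governs, enrolling that patient is a major violation, which section 12.3.2 requires to be notified to the IRB within 24 hours and reported within 10 business days. If the 90 mmHg sentence is an exception, the patient is eligible.

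The exception reading also runs in an odd direction. It would set the lower floor for patients who already take BP-lowering drugs, and the protocol gives no reason for doing so.

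**Working it through.** The plan offers no figure to reproduce. The check is a comparison of thresholds, using whole-number readings.

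**Inputs**

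- General exclusion: systolic below 100 mmHg (section 5.2), so eligible at 100 or more.
- Condition for patients on other BP drugs: systolic above 90 mmHg (section 5.2), so 91 or more.
- Hold rule for study drug: systolic below 90 mmHg (section 6.4.6), so 89 or less.

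**Reading A: every exclusion applies independently.** Anyone below 100 is out. Anyone at 100 or more is already above 90. The 90 mmHg condition admits nobody and excludes nobody.

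**Reading B: the 90 mmHg sentence is a specific exception.**

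- Patients on other BP drugs may enter from 91. Patients on none need 100. The band opened is 91 to 99.
- Margin above 90: 91 - 90 = 1 mmHg, up to 99 - 90 = 9 mmHg. At the general floor it is 100 - 90 = 10 mmHg.
- The hold applies below 90, so a reading of exactly 90 does not trigger it. The fall needed to reach 89 is 91 - 89 = 2 mmHg at the bottom of the band, 99 - 89 = 10 mmHg at the top, and 100 - 89 = 11 mmHg at the general floor.

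**Reading C: 90 mmHg is an on-study limit for continuing other BP drugs.** The number matches the hold level, which makes this plausible. But the sentence stands among the entry exclusions, follows directly on a criterion about current use at entry, and has no counterpart in sections 6.5 or 6.6. If this was the intent, the sentence is misplaced.

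The condition is therefore redundant under A, sets an unexplained lower floor under B, and belongs elsewhere under C. The wording needs correcting in each case.

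**The case against.** The strongest reply is that there is no true conflict. In a list of exclusions any one suffices, the 100 mmHg bullet is unqualified, and a sentence saying which other drug classes are acceptable does not lift a separate exclusion. On that view a patient at 91-99 mmHg is simply excluded. This stands as the ordinary reading, and a reader should not infer that the protocol definitely admits such patients. It does not remove the defect: the sentence states a BP value, and that value does nothing at entry unless it is read as an exception, so the text invites that reading.

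A second reply is that harm is limited elsewhere. Participants measure BP daily and must call and stop study drug below 90 mmHg (6.4.6). The nurse makes contact daily, or at least three times, in the first week (6.4.7). The investigator may decline anyone for whom participation seems inadvisable (5.2). All of this stands and keeps the point small, but none of it says which floor applies at entry.

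Two stronger inferences are tempting and not supported:

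- **That patients entering at 91-99 mmHg would be driven below 90.** Section 2.2.2 cites a placebo-subtracted fall of "9 to 13/6 to 8 mmHg for 40 mg", but in patients with mild to moderate hypertension and diastolic pressure of 95-114 mmHg. The document gives no effect at systolic 91-99 mmHg, and it may be smaller. Setting the margins against that fall would not measure harm.
- **That a low reading could be met only by holding or stopping study drug.** Section 6.1.6 says "There is no dose reduction or escalation for this study", but this fixes only the study-drug dose. Section 6.5 allows usual medications to continue without requiring it, so another BP drug could be reduced or stopped.

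**Conclusion.** The inconsistency is real and minor. Section 5.2 carries two systolic thresholds that no other section reconciles. The most likely consequence is a redundant condition. The less likely one is entry at 91-99 mmHg for patients already on BP-lowering drugs, 1-9 mmHg above 90.

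That band depends on the exception reading and on whole-number measurements. The document does not say how many participants would fall in it. That they are few of 40 is a judgement, since it takes both current use of a permitted BP drug and a systolic pressure under 100 mmHg.

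This is an eligibility and safety wording matter. A reader might take it as a threat to the efficacy analysis, but the choice of floor does not alter the definition of the primary endpoint, the proportional odds model or the sample size of 40.

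**What to change.** In section 5.2, keep the 100 mmHg exclusion for everyone and replace the 90 mmHg sentence with: *Other blood pressure medications are permitted, subject to the systolic BP criterion above.* Every participant then enters at least 10 mmHg above 90.

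If the sponsor does want a lower floor for patients on other BP drugs, it should be written as an explicit exception within the 100 mmHg bullet, with the reason. If 90 mmHg was meant as an on-study limit, it should move to section 6.5 and be worded as such.

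The cost is one sentence in a protocol amendment, with no new measurement, visit or analysis.

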5.3 STRATEGIES FOR RECRUITMENT AND RETENTION

Information about the study will be circulated widely to community physicians and medical establishments. Information about the availability of the study may be distributed at SARS-CoV-2 test sites or made known by public advertisement including by web. All advertisement materials will be approved by the UH Human Subjects Committee prior to its use.

To compensate participants for time and effort, participants will be given \$60 at each study visit, for a maximum of \$240 total (\$60 x 4 visits) for participation in the study.

5.4 PARTICIPANT WITHDRAWAL OR TERMINATION

5.4.1 REASONS FOR WITHDRAWAL OR TERMINATION

Each participant may discontinue study drug and/or withdraw completely from the study for any reason. The date and reason for termination or withdrawal will be documented.

Premature Termination of Study Drug for a study participant may occur for the following reasons:

- Possible drug-related AE or toxicity which, in the judgment of the PI or Sub-I, is considered to not be in the subject's best interest
- Request by the subject to terminate study drugs
- Subject cannot make scheduled visit(s)
- Subject does not provide OP or blood sample(s)

Withdrawal completely from the study may occur for the following reasons:

- Failure to comply with the provisions of the protocol
- Request by the subject to withdraw.

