5.4.2 HANDLING OF PARTICIPANT WITHDRAWALS OR TERMINATION

Participants may withdraw or terminate involvement at any time for any reason, and that request will be honored.

No discontinuation visit is necessary. However, participants who terminate or withdraw for toxicity reasons will be followed for that toxicity until the toxicity is resolved.

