6.4.10 DISCONTINUATION OF STUDY TREATMENT

The study treatment will be prematurely discontinued for the following reasons:

- Participant becomes pregnant or starts breast-feeding
- Participant is admitted to the hospital
- Participant requires a prohibited medication

The participant will be asked to continue to be followed and attend the study visits after discontinuation of study treatment. No study procedures will be performed on the participant during hospitalization.

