9.3 DESCRIPTION OF STATISTICAL METHODS

9.3.1 GENERAL APPROACH

This is a prospective, randomized, double-blind 3-week study of telmisartan vs placebo in symptomatic individuals diagnosed with COVID-19 disease. Subjects will be randomized 1:1 to receive telmisartan vs placebo for 3 weeks (21 days). A block randomization will be applied to ensure the balance of participant numbers and baseline severity between treatments.

The baseline characteristics of participants will be summarized by descriptive statistics and compared between the two groups to check any imbalance. The primary efficacy endpoint for the study is an ordinal outcome corresponding to the maximum clinical status of the study subject. The proportional odds model and logistic regression techniques will be applied to compare the ordinal outcome between treatments, based on odds ratios. There are several secondary efficacy endpoints defined for the study. For those measures, averages and rates will be compared between groups, appropriately. Longitudinal mixed-effects models will be utilized to handle longitudinal outcome measures observed at days 1, 4, 10, and 21. The covariate use in regression models will be limited due to the relatively small sample size. Tests of normality will be performed on continuous data and transformation applied where applicable. Type-I error for hypothesis tests will be fixed at 5% nominal level. All efficacy and safety estimates (e.g.

average and proportions) will be provided with 95% confidence intervals (95% CI). The multiplicity error in exploratory analyses will be corrected via the false discovery rate. All efforts will be taken to minimize loss-to-follow-up. However, small amounts of missing data may occur. In such cases, participants without final outcome data will be excluded from the analysis. Sensitivity analysis with multiple imputations will be performed for confirming results. Statistical analyses will be performed using the R software 3.5.1 version.

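### The team may withdraw a participant completely for non-compliance, and nothing then keeps primary-outcome collection going, so outcomes can be lost, plausibly for reasons tied to illness

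*Combined protocol and SAP*

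**What the plan says.** Section 5.4.1 has two lists. The first gives reasons for stopping study drug: a possible drug-related event, the participant's request, inability to make visits, and missing swab or blood samples. The second gives reasons for leaving the study completely: the participant's request, and "Failure to comply with the provisions of the protocol". Both lists are permissive, since the events may occur. No threshold for non-compliance is given.

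Section 5.4.2, whose heading covers withdrawal and termination alike, says "No discontinuation visit is necessary". The only follow-up it names is that "participants who terminate or withdraw for toxicity reasons will be followed for that toxicity until the toxicity is resolved".

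Section 6.4.10 gives a different list of reasons for stopping treatment (pregnancy or breast-feeding, hospital admission, a prohibited medication) and then says "The participant will be asked to continue to be followed and attend the study visits after discontinuation of study treatment". It adds "No study procedures will be performed on the participant during hospitalization".

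On analysis, section 9.2 defines the dataset as enrolled subjects with data from entry to the day 21 visit. Section 9.3.1 says "participants without final outcome data will be excluded from the analysis", with multiple imputation as a sensitivity analysis and no imputation model described.

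**The concern.** The protocol asks participants to record blood pressure, temperature and symptoms daily, to take study drug, and to attend four visits. A participant who feels too ill to do this may look non-compliant. If the team then withdraws that person, follow-up ends although consent has not been withdrawn, and the analysis rule removes the person from the primary comparison. Such loss would be avoidable and possibly related to the outcome itself.

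Loss could also differ by arm. Section 2.2.2 reports placebo-subtracted systolic falls of 9 to 13 mmHg at 40 mg, and section 6.4.6 tells participants to hold study drug if systolic pressure falls below 90 mmHg. Interruptions could therefore be commoner on telmisartan. For toxicity cases, section 5.4.2 secures follow-up of the toxicity and does not mention the primary outcome. In a trial of 40, a handful of missing outcomes is enough to matter.

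**Working it through.** **1. Passages side by side.**

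| Situation | What the protocol says about later outcome collection |
|---|---|
| Complete withdrawal for non-compliance (5.4.1) | Nothing requires it |
| Drug stopped for toxicity (5.4.1) | 5.4.2: followed for that toxicity |
| Drug stopped for missed visits, missing samples or request (5.4.1) | No explicit rule in 5.4.1 or 5.4.2; the general sentence in 6.4.10 might apply, but it follows a different list |
| Drug stopped on admission (6.4.10) | Asked to stay in follow-up; 4.1.1 scores maximum severity before discharge; 6.4.6 asks for a records release at entry |

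**2. The plan's own power figure.** Inputs from section 9.4: 20 per arm, placebo probabilities {0.40, 0.40, 0.05, 0.04, 0.04, 0.04, 0.03}, odds ratio 5. From sections 9.3.1 and 9.3.2: 5% type I error, one-sided test. The printed telmisartan vector has six entries summing to 0.99, so the arm was derived from the placebo vector. With placebo cumulative probability C, the telmisartan cumulative probability is 5o/(1+5o), where o = C/(1-C).

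- Category 1: o = 0.40/0.60 = 0.667; 5o = 3.333; probability 3.333/4.333 = 0.769.
- Categories 1-2: o = 0.80/0.20 = 4; 5o = 20; cumulative 20/21 = 0.952, so category 2 has 0.952 - 0.769 = 0.183.
- The rest follow in the same way: 0.014, 0.010, 0.009, 0.009, 0.006.

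The test is the proportional-odds score test. With midranks, W is the rank sum on telmisartan, E = n2(N+1)/2, and V = (n1·n2/12)[(N+1) - Σ(m³-m)/(N(N-1))], where m is the number of participants in each category. Reject if (W-E)/√V < -1.645. Over 40,000 simulated trials, power is 0.80 one-sided, which reproduces the stated figure. It is 0.69-0.70 two-sided. With the printed telmisartan vector and an assumed seventh entry of 0.01, one-sided power is 0.77.

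**3. How few severe outcomes there are.** Categories 3-7: placebo 20 × 0.20 = 4; telmisartan 20 × (1 - 0.952) ≈ 1.

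**4. Illustrative loss.** All loss rates are assumed. A lost participant is dropped, as 9.3.1 specifies.

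| Loss pattern | Rate | One-sided power |
|---|---|---|
| None | 0 | 80% |
| Even across arms and severity | 5 / 10 / 15 / 20% | 78 / 77 / 74 / 72% |
| Categories 2-7, both arms | 10 / 20 / 30% | 78 / 75 / 72% |
| Categories 3-7, both arms | 25 / 50% | 77 / 73% |

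| No drug effect, loss on telmisartan only | Rate | One-sided type I error |
|---|---|---|
| None | 0 | 5% |
| Categories 2-7 | 10 / 20 / 30% | 7 / 9 / 12% |
| Categories 3-7 | 25 / 50% | 8 / 13% |

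The category 2-7 rows come nearer the likelier route, because they include symptomatic participants who are never admitted. With no drug effect, 10-30% of that group is 20 × 0.60 × 0.10 = 1.2 to 20 × 0.60 × 0.30 = 3.6 people in one arm. The category 3-7 rows at 25-50% are 20 × 0.20 × 0.25 = 1 to 20 × 0.20 × 0.50 = 2 people.

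**The case against.** A good deal can be said for the plan.

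- A reader might infer that 5.4.2 and 6.4.10 contradict each other. They do not. Section 5.4.2 waives a special exit visit and is silent on scheduled visits, the log and phone contact. The 6.4.10 sentence is general enough to be read alongside it. What remains is a gap: no explicit rule for efficacy follow-up after the non-toxicity drug stops in 5.4.1.
- A reader might infer that missing a visit leads to complete withdrawal. Section 5.4.1 places missed visits and missing samples under stopping study drug. Ending all follow-up takes a further, discretionary decision.
- A reader might infer that hospitalised participants are the ones lost. They are the best protected: 4.1.1 scores them on maximum severity before discharge, 6.4.6 asks for a records release, and 6.4.10 asks them to stay in follow-up.
- Other safeguards exist: visits at other venues (6.4.6), nurse contact at least three times in the first week (6.4.7), tabulated withdrawals with reasons (9.3.5), and the imputation sensitivity analysis. Because the endpoint is a maximum from day 3, a partly kept log still carries information.

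All of this stands, and it narrows the point. It does not remove it: none of these provisions expressly covers someone already withdrawn for non-compliance, and none overrides 9.2 and 9.3.1.

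**Conclusion.** The plan contains a stated rule under which the team can end outcome follow-up without withdrawn consent, and an analysis rule that then drops the participant. Primary outcomes can therefore be lost, chiefly among non-hospitalised participants who stop keeping the log. That this loss would track illness is plausible but is inference; the documents report no rate or pattern.

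Under the assumed rates the cost is a few points of power if loss is similar in both arms, and a one-sided type I error of roughly 7-13% if it falls on telmisartan alone. These figures show sensitivity and are not forecasts. The category 3-7 scenarios in particular assume loss in the group that the protocol already covers. A reading in which outcomes will be lost, or in which severe cases will be, goes beyond the text.

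This is a preventable weakness in a small pilot sized on feasibility. It does not invalidate the design.

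**What to change.** - In 5.4.1, remove failure to comply as a reason to end outcome follow-up, so that only withdrawn consent ends it.
- In 5.4.2, state, consistently with 6.4.10, that participants who stop drug, miss visits or are non-compliant continue outcome collection to day 21 by log, nurse phone call or hospital record.
- In 9.2 and 9.3.1, include these participants in the primary analysis, say how a partly kept log is scored, and specify the imputation model for outcomes that are still missing.
- The drug-stopping reasons in 5.4.1 and 6.4.10 are for the sponsor to reconcile; none is proposed here.

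The cost is an amendment to the wording, with the usual ethics approval, and a few extra calls by the existing nurse. The log, the calls and the records release are already in the protocol, and the primary endpoint can be scored without clinic attendance.
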